3.3 Inclusion of Women and Minorities

Both men and women of all races and ethnic groups are eligible for this trial.

3.4 Source of Patients

This will be a multi-center study. Each study center is required to obtain Institutional Review Board (IRB) approval to conduct the study before enrollment of patients may commence. Patients meeting the entrance criteria who are known or referred to the study center will be eligible for enrollment.

4. REGISTRATION PROCEDURES

4.1 General Guidelines

Eligible patients will be entered on study by the coordinating center study team at Columbia University Medical Center (CUMC). Subsites will fax or PDF/e-mail their signed eligibility checklist to the coordinators at CUMC. Once received, CUMC will confirm eligibility, enter the patient into the CUMC Cancer Center database and assign a study ID number to each patient. CUMC will provide the subsite with the information and the patient will be enrolled to the study.

Following enrollment, patients should begin protocol treatment within 10 days. Issues that would cause treatment delays should be discussed with the Principal Investigator. If a

patient does not receive protocol therapy within the specified timeframe, the patient's enrollment on the study may be canceled.

4.2 Screening

All potential study patients will be screened and eligibility determined prior to enrollment. Unless otherwise specified, the following procedures and evaluations will be performed as noted in the study calendar (Section 9) prior to the start of study drugs (cycle 1, dose 1):

- 1) Obtain written informed consent and privacy authorization prior to initiating any protocol-required procedure that is not considered standard of care
- 2) Review eligibility criteria
- 3) Review medical chart for past medical/surgical history
- 4) Record medications and prior treatment regiments
- 5) Record response to prior treatment regimen
- 6) Document histopathology from:
 - i. Original diagnosis
 - ii. Tumor biopsy in the relapsed setting (if applicable)
- 7) Documentation of known measurable disease parameters by the following procedures:
 - i. CT of neck, chest, abdomen, and pelvis (PET/CT optional)
 - ii. Skin exam
 - iii. Other imaging techniques documenting disease site other than neck, chest, abdomen, and pelvis, if applicable
- 8) Obtain a 12-lead electrocardiogram (ECG) and calculate the QTc interval.
- 9) Perform a comprehensive physical examination
- 10) Assess and record ECOG or Karnofsky Performance Status
- 11) Local laboratory: Collect blood for hematology (CBC with differential counts), chemistry (Na, K, Cl, HCO₃, BUN, creatinine, glucose, calcium, magnesium, including serum β -human chorionic gonadotropin [β -hCG] pregnancy test for women who are not postmenopausal or surgically sterile [within 7 days prior to cycle 1, dose 1 and again within 24 hours prior to first dose of the study drugs.], liver function tests (total protein, Albumin, AST, ALT, total bilirubin, direct bilirubin, alkaline phosphate).
- 12) Calculate creatinine clearance using the glomerular filtration rate (GFR) according to the Cockcroft and Gault Equation, only if screening serum creatinine is > Upper Limit of Normal: $GFR^* = (140 - \text{age [years]}) \times \text{actual body weight (kg)} / 72 \times \text{serum creatinine}$
*For female patients, multiply by 0.85
- 13) Urinalysis

4.3 Informed Consent

4.3.1 Study Informed Consent

Study personnel must obtain documented consent from each potential patient prior to conducting any study related procedures and enrolling the patient to the clinical study. Any procedures/tests performed prior to giving written informed consent may be used provided that these tests are considered part of standard care. Consent must be documented on the IRB approved consent form by obtaining the dated signature both of the patient and of the investigator conducting the consent discussion. If the patient is unable to sign the consent form, then oral consent, attested to by the dated signature of an impartial witness (someone not involved with the conduct of the study), is the required alternative.

If the patient is illiterate, an impartial witness should be present during the entire informed consent reading and discussion. Afterward, the patient should sign and date the informed consent, if capable. The impartial witness should also sign and date the informed consent along with the individual who read and discussed the informed consent (i.e., study staff personnel).

The information from the consent form should be translated and communicated to the subject in language understandable to the subject. When the study participant is non-English the consent form must be read accurately in its entirety by a qualified professional translator. The translator will provide a written statement indicating that the consent form has been accurately translated from the accompanying English version, and that the study participant consents to participation. The professional translator will sign the consent form as an impartial witness.

A copy of the signed and dated consent form should be given to the patient before participation in the study.

The initial informed consent form and any subsequent revised written informed consent form, and written information will receive IRB approval prior to implementation. The patient or his/her legally acceptable representative will be informed in a timely manner if new information becomes available that may be relevant to the patient's willingness to continue participation in the trial. The communication of this information will be documented.

4.4 Registration Process

To register a patient, the following documents should be completed by a member of the research staff and sent to the study coordinator at CUMC:

- Eligibility Screening Worksheet
- Copy of required laboratory and imaging tests

The Study Coordinator will verify eligibility. To complete the registration process, the Coordinator will:

- Assign a patient study number
- Register the patient on the study
- Confirm registration with the Principal Investigator

No patient may be enrolled or begin treatment prior to registration and assignment of a patient number. Patients who are registered but not treated will be replaced. Investigators will be notified by CUMC when enrollment in the initial part of the study(stage 1) is closed and enrollment into the next parts of the study (stage 2 and expansion cohort) can begin. Investigators will be notified by CUMC or the Sponsor if the study is placed on administrative hold, when it is completed, or is closed to further patient enrollment.

4.5 Withdrawal and Replacement of Patients

Patients will be informed that they have the right to withdraw from the study at any time for any reason, without prejudice to their medical care. The Investigator also has the right to withdraw patients from the study for any of the following reasons:

- Progression of Disease.
- Occurrence of an unacceptable adverse event.
- Patient requires use of an unacceptable concomitant medication.
- General or specific changes in the patient's condition unacceptable for further treatment in the judgment of the Investigator.
- Non-compliance.
- Patient withdrawal of consent.
- Patient no longer meets the protocol entrance criteria.
- Sponsor request.

At the time of withdrawal, all study procedures outlined for the End of Study Visit should be completed. The primary reason for a patient's withdrawal from the study is to be recorded in the patient's chart and the CRF.

Patients who discontinue from the study will not be replaced.

Patients who miss >10% of planned dose will be censored for response assessment, but not for toxicity, and will be replaced for adequate response assessment.

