5.5 Duration of Follow Up

Patients will have an end of study visit 4 weeks +/- 7 days after their last dose of drug to evaluate safety. Patients will be further followed every three months after the 4-week safety evaluation for one year, or until they develop a POD or begin a new treatment for their disease, for evaluation of delayed toxicity. Patients removed from study for unacceptable adverse events will be followed until resolution or stabilization of the adverse event.

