6. DOSING DELAYS/DOSE MODIFICATIONS

6.1 Dose Delays

- Study drugs will be held until adverse event returns to \leq Grade 2.
- If interruption lasts for more than 14 days, study treatment will be discontinued.
- In patients who miss $>10\%$ of planned dose in the Phase II, but not the Phase Ib, data will be censored for response, but not for toxicity, and patients will be replaced for adequate response assessment.

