10.3 Assessment of Disease Response

After discontinuation of therapy, patients are to have disease response assessed at the discretion of the treating physician, but not longer than every 6 months. Bone Marrow biopsy will be required after cycle 2 for patients with bone marrow involvement at baseline who have a complete response by imaging and physical exam

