10.3.1 Definitions

Evaluable for objective response. Patients who have received at least one day of therapy, and have had their disease re-evaluated will be considered evaluable for response. These patients will have their response classified according to the definitions stated below. Patients who exhibit objective disease progression prior to the end of cycle 1 will also be considered.

Measurable disease. Measurable lesions are defined as those that can be accurately measured in two dimension (longest diameter to be recorded) as ≥ 20 mm with conventional techniques (PET/CT, MRI, x-ray) or as ≥ 10 mm with spiral CT scan. All tumor measurements will be recorded in millimeters (or decimal fractions of centimeters). Tumor volume will be recorded as the sum of the product of the diameters (SPD) of the largest predominant target lesions.

FDG avidity is based on comparison with background tissues. There is no specific SUV value that is considered a cut-off.

Non-measurable disease (evaluable disease). All other lesions (or sites of disease), including

small lesions (<10 mm using spiral CT scan), are considered non-measurable disease. Bone lesions, leptomeningeal disease, ascites, pleural/pericardial effusions, lymphangitis cutis/pulmonitis, inflammatory breast disease, abdominal masses (not followed by CT or MRI), and cystic lesions are all non-measurable.

Target lesions. All measurable lesions up to a maximum of 6 lesions total, representative of all involved organs, should be identified as target lesions and recorded and measured at baseline. Target lesions should be selected on the basis of their SUV avidity (High SUV lesions will be prioritized, even if not the largest lesions) and size (lesions with the largest SPD diameter) and their suitability for accurate repeated measurements (either by imaging techniques or clinically). An SPD for all target lesions will be calculated and reported as the baseline sum SPD. The baseline sum SPD will be used as reference by which to characterize the objective tumor response based on CT criteria.

Non-target lesions. All other lesions (or sites of disease) including any measurable lesions over and above the 6 target lesions should be identified as non-target lesions and should also be recorded at baseline. Measurements of these lesions are not required, but the presence or absence of each should be noted throughout follow-up.

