12.3.2 Phase II

12.3.2.1 Primary Objective: Activity Analysis

Efficacy endpoints in this study include defining the proportion of patients with disease response (CR+PR).

CR, PR, and SD are to be determined according to the International Harmonization Project revised Criteria (2007), Patients who discontinue the study before response evaluation will be considered un-evaluable.

In the expansion cohort, analysis for activity in mantle cell lymphoma will be measured for proportion of patients with disease response (CR+PR) determined according to the International Harmonization Project revised Criteria (2007). Patients who discontinue the study before response evaluation will be considered un-evaluable.

For responding patients, the duration of response and time to progression will be reported on a per-patient basis.

Data that may further characterize the activity of ACY-1215 will be summarized and assessed for a potential dose-response relationship.

Overall response rates will be estimated upon completion of the study along with exact 95% confidence intervals.

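### Treated Phase II patients drop out of the response-rate denominator because of events after treatment starts, and some are replaced, so the primary ORR and the Simon decision can be biased

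*Combined protocol and SAP*

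**What the plan says.** Objective response (CR + PR) is the primary Phase II endpoint. Two rules take treated patients out of it.

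- **Missed dose.** Section 4.5: "Patients who miss >10% of planned dose will be censored for response assessment, but not for toxicity, and will be replaced". Section 6.1 limits the rule to Phase II and says "data will be censored for response, but not for toxicity, and patients will be replaced for adequate response assessment".
- **Leaving early.** Section 12.3.2.1, for both the main study and the mantle cell (MCL) cohort: "Patients who discontinue the study before response evaluation will be considered un-evaluable". Section 4.5 says that patients who discontinue are not replaced.

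Other sections bear on who counts:

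- Section 10.3.1 sets no dose threshold: "Patients who have received at least one day of therapy, and have had their disease re-evaluated will be considered evaluable for response". It adds: "Patients who exhibit objective disease progression prior to the end of cycle 1 will also be considered".
- Section 10.4.3 takes best response from the start of treatment, and 10.4.4 bases the ORR on each patient's best response.
- Section 12.8 refers only to the Simon methodology. Section 12.10 keeps available activity data in listings and tabulations but rules out imputation. Section 12.11 defers a formal analysis plan to before database lock.
- Section 10.3: "After discontinuation of therapy, patients are to have disease response assessed at the discretion of the treating physician", at intervals of at most six months. Section 5.5 has three-monthly follow-up for a year, "or until they develop a POD or begin a new treatment for their disease".

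**The concern.** The Simon cut-offs assume 22 and then 40 patients who were not selected on what happens after treatment starts. Here a patient's place in the denominator can depend on toxicity, deterioration or withdrawal. If the patients removed would have responded less often, the ORR is overstated. Where they are also replaced, the success count is filled from a more favourable group, and an inactive drug passes more often.

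The >10% rule is the larger problem because its terms are undefined:

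- It has no time window.
- It does not say whether a toxicity hold, or the reduction to 75% of dose in Table 2 (6.3.1), counts as missed dose.
- With no window, a late hold could erase a response already recorded, against 10.4.3.
- Section 10.3.1 would call the same patient evaluable, and no section says which rule prevails.

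The early-leaver gap is narrower. Sections 5.5, 10.3 and 10.3.1 provide for assessment after treatment stops and for early documented progression. What remains is mainly death, withdrawal or new therapy before any re-evaluation.

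**Working it through.** **1. The design.** Section 12.1.2 gives 22 + 18 = 40 patients and continuation at 2 or more responses in 22. I read the 8 responses in 5.1.2 as at least 8 of 40 in total. For true rate q,

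P(declare active) = Σ(x = 2..22) Bin(x; 22, q) · P(Bin(18, q) ≥ 8 − x).

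A minimax search at 10% versus 25%, α 0.05 and power 0.80 returns 22/40, continuing at ≥3 and succeeding at ≥8, with α 0.0398 and power 0.8032. With the written ≥2 of 22, these are 0.0416 and 0.8161. At the printed null of 15% the written rule gives 0.2427. That is a separate defect, so I use 10% as the reference and show 15% only as a check on direction.

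**2. Replacement.** Let p be the true all-treated ORR, f the share of treated patients replaced, and k the response rate of those replaced relative to the overall rate. The counted patients respond at

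q = p(1 − fk)/(1 − f).

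The documents give neither f nor k, so both are shown as ranges. For p = 0.10, each cell gives q, then P(declare active):

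| k | f = 5% | f = 10% | f = 20% | f = 30% |
|---|---|---|---|---|
| 0 | 0.1053, 0.054 | 0.1111, 0.070 | 0.1250, 0.118 | 0.1429, 0.203 |
| 0.5 | 0.1026, 0.047 | 0.1056, 0.054 | 0.1125, 0.074 | 0.1214, 0.104 |
| 1 | 0.1000, 0.042 | 0.1000, 0.042 | 0.1000, 0.042 | 0.1000, 0.042 |
| 1.5 | 0.0974, 0.036 | 0.0944, 0.031 | 0.0875, 0.021 | 0.0786, 0.011 |

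The probability passes 0.05 at f of about 3.6% (k = 0) or 7.0% (k = 0.5). At p = 0.15 the direction is the same: with f = 10% and k = 0, 0.243 becomes 0.345.

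**3. Unreplaced leavers.** With the success counts fixed, these do not raise the false-positive rate; they only shrink the denominator of the reported ORR. As an illustration, assume 20% leave and none respond (exact 95% CIs):

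- Main study, eight leavers: 8/40 = 20% (9.1–35.6%) becomes 8/32 = 25% (11.5–43.4%).
- MCL cohort, four leavers: 4/20 = 20% (5.7–43.7%) becomes 4/16 = 25% (7.3–52.4%). This cohort has no success threshold, so only its estimate is affected.

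**4. How easily the >10% rule is triggered.** A cycle is 28 or 56 doses, and missed doses are not made up (treatment plan common to both phases). If the window is one cycle and held doses count as missed, three days suffice: 3/28 = 6/56 = 10.7%. Over two cycles it takes six days: 6/56 = 12/112 = 10.7%. Section 6.1 ends treatment only after a longer gap ("If interruption lasts for more than 14 days, study treatment will be discontinued"), and Table 2 directs holds for Grade 3–4 toxicity. On that reading, a patient managed exactly as the protocol directs can be removed from the primary endpoint.

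**The case against.** - **Estimand.** Section 6.1 says replacement serves adequate response assessment, which suggests that interest lies in adequately dosed patients. If the null and the 25% target describe that group, the false-positive rate is not inflated. This stands as a condition on the result. The documents do not state that population, and 10.3.1 points the other way.
- **Who is replaced.** Section 4.5 does not replace patients who discontinue. The likeliest non-responders may therefore be unreplaced leavers, for whom the false-positive rate does not rise. A patient can be both a discontinuer and a >10% misser, and the text does not resolve the overlap. The k = 0 row is thus an extreme case, especially at f = 20–30%.
- **The null.** The 0.05 crossings belong to an inferred 10% null. At the printed 15% the rule already exceeds 0.05 with no exclusions. Only the direction carries over.
- **Meaning of missed.** Section 12.5 mentions missed or held doses and dose reductions as distinct items, so holds may not count as missed. Against that, 6.1 places the rule under dose delays, beside the hold rules.
- **Likely size of f.** Sections 2.2.15 and 7.3.3 report no Grade 4 events and no discontinuations for adverse events on monotherapy. That is 15 myeloma patients on a schedule with treatment breaks, so it says little about f here.
- **Later plan.** The deferred plan could add an all-treated ORR, and 12.10 keeps the data. It could not undo replacements or a Stage 2 decision already made.

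**Conclusion.** The concern holds and should be fixed before the response data are used. As written, the plan lets events after treatment starts decide who is in the primary-endpoint denominator, and its sections on who is evaluable conflict with no order of precedence. That conclusion does not depend on how the removed patients respond.

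The size and direction of the bias do. Upward bias in the ORR needs the removed patients to respond less often than the rest, which is plausible when doses are missed through toxicity or deterioration but is not shown in the documents. A higher false-positive rate needs, in addition, replacement and a null that describes all treated patients. Under those conditions, with a 10% null and 5–30% replaced, 0.042 becomes 0.047–0.104 at half the overall response rate and 0.054–0.203 if none respond.

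**What to change.** - Define the primary response population as all Phase II patients who receive at least one dose: the first 22 and first 40 treated for the Simon decisions, and all treated patients in the MCL cohort.
- Count treated patients without a documented CR or PR as non-responders.
- Delete response censoring and replacement of treated patients from 4.5 and 6.1. Keep replacement only for patients registered but never treated, as 4.4 already provides. Align 10.3.1, 10.4.4, 12.3.2.1 and 12.8.
- Report the dose-adherent, re-evaluated subset as a sensitivity analysis. State its 10% window and whether protocol-directed holds and reductions count as missed dose.
- State which population the 25% target describes, and recheck the sample size.

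**Cost.** Wording changes, a possibly less favourable ORR, and perhaps power. If 25% was meant for adequately dosed patients, the all-treated rate is 0.25(1 − f + fk), with k here relative to the retained patients. For f = 5/10/20/30%, power falls from 0.816 to 0.765/0.704/0.561/0.399 if none of the others respond (rates 0.2375/0.225/0.20/0.175). At half the retained rate it falls to 0.791/0.765/0.704/0.636. Fewer patients are enrolled because treated patients are no longer replaced. No dosing or hold rule changes.

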5. TREATMENT PLAN

5.1 Overall Design and Plan of the Study

5.1.1 Phase Ib:

This is a Phase Ib two-arm multicenter, open-label study in patients with relapsed/refractory lymphoma. The phase Ib will be conducted to determine the safety and tolerability of two dosing schedules of ACY-1215 monotherapy in patients with lymphoid malignancies. Patients will be accrued sequentially to two dose cohorts (Arm A and then after a safety assessment has occurred, Arm B) of ACY1215. All patients will take the assigned dose of ACY1215 orally for 28 consecutive days. Patients enrolled into Arm A will take ACY1215 160 mg daily, whereas patients enrolled into Arm B will take ACY1215 160 mg twice daily. ACY-1215 will be supplied as a liquid for oral administration (PO). Each dose will be administered at least 1 hour after ingestion of food followed by at least 4 ounces of water. Patients will be instructed not to ingest food or other oral medication for at least 2 hours after each ACY-1215 dose. Three

patients will be sequentially enrolled in one of two cohorts: Arm A and then after a safety assessment has occurred, Arm B for a total of six patients (3 in each arm). If $\leq 33\%$ of patients ($N \leq 1$) experiences a dose limiting toxicity (DLT) in a cohort, the cohort will be expanded to 6 patients. If there are $\leq 33\%$ ($N \leq 2$ DLTs), the cohort will be further expanded to a total of 10 patients ($3+3+4$). The total number of patients for both Arms A and B with full expansions will total of 20. If more than 1/3 or 2/6 patients experience a DLT, there will be no expansion. Safety data obtained from this Phase Ib will be analyzed by the sponsor and collaborating investigators to recommend a Phase II dose.

5.1.2 Phase II:

This is a phase II, single-arm, multicenter, open-label study in patients with relapsed or relapsed/refractory lymphoma. Utilizing the Simon 2 Stage Minimax design, an estimated 40 patients will be needed to determine efficacy at a power of 0.80 and type I error of 0.05. Using this design, there will be an early stopping rule if $< 10\%$ achieve a response in Stage 1. Twenty-two ($N=22$) patients will be accrued to Stage 1, of which 2 patients are required to achieve a response to allow accrual to Stage 2. Patients accrued to Stage 1 of the Phase II will be of all lymphoid malignancy subtypes including those with mantle cell lymphoma (MCL). Eighteen patients ($N=18$) will be treated in Stage 2, of which 8 responses would be needed to attain an efficacy of at about 25%. The safety, tolerability, single- and multiple-dose PK, pharmacodynamics, and anti-tumor activity of ACY-1215 also will be evaluated. Simultaneously in Stage 2, an additional cohort of 20 mantle cell lymphoma patients will be assessed to evaluate for a signal of efficacy in this subtype. These patients will be enrolled in parallel to the phase II study. Assuming success in Stage I, enrollment to Stage 2, and expansion of MCL cohort, the total number of patients will be 60 (Stage 1 $N=22$, Stage 2 $N=18$, MCL focused Expansion Phase $N=20$).

5.1.3 Treatment plan common to both Phase Ib and Phase II:

After executing written informed consent, patients will be evaluated for study eligibility during the Screening period within the Screening period before Cycle 1, Day 1 [C1D1]. Patients determined to be eligible will be treated on study. Patients will be evaluated on Days 1, 8, and 15 of Cycle 1.

On study drug administration days that coincide with scheduled study center visits, ACY-1215 will be administered at the study center.

- One cycle of therapy is comprised of 28 or 56 doses of ACY-1215.
- Administration of the study drugs will be allowed within 48 hours of the scheduled dates.
- Missed doses will not be made up.

Patients will be evaluated for disease response with CT or PET/CT after cycles 2 and 6, then at the investigators discretion with intervals no more than 6 months. Patients who withdraw from the study will be required to have an End of Study Visit 4 weeks (+/- 7 days) after the last study drug dose. After discontinuation of therapy, patients will be followed on an approximately every 3 month basis (+/- 1 week) until development of PD or initiation of alternative therapy in order to determine the duration of response.

Safety will be evaluated during the study by documentation of AEs and SAEs, clinical laboratory tests (hematology, clinical chemistry, and urinalysis), physical examinations, vital sign measurements, and 12-lead ECGs.

The anti-tumor activity of ACY-1215 will be determined by CT or PET/CT and assessment of disease response will be evaluated using the International Harmonization Project revised Criteria (2007) [27].

Exposure-response of ACY-1215 including biomarkers relating to intracellular protein acetylation, IL6 and IL10 secretion, and markers of the UPR will be analyzed as a function of treatment and response.

Serial blood samples will be collected for determination of the single- and multiple-dose PK of ACY-1215. Patients will receive ACY-1215 160mg orally (PO) for 28 consecutive days per cycle according to schedule determined by the Phase Ib. There will be no limit to the number of cycles patients will receive.

Table 1: Regimen Description

REGIMENT DESCRIPTION						
Agent	Premedications; Precautions	Dose	Route	Frequency	Schedule	Cycle Length
ACY-1215	None	160mg (1 vial)	PO	Once daily vs. Twice daily	Days 1-28	28 days

